#### **5.6.4.** Dietary and Lifestyle Restrictions

The following foods and products will be prohibited from 14 days before Day 1 of Cycle 1 until EOT:

• Foods containing hypericum perforatum (Saint John's wort)

The following foods and products will be prohibited from Day 1 of Cycle 1 until EOT:

• Foods or beverages containing grapefruit

For Japanese sites, subjects will be hospitalized during Day 1 to Day 21 on Cycle 1 of the Dose Escalation Part.

Female subjects of child bearing potential or those who have been amenorrheic for 12 months or longer for medical reasons other than sterilization surgery (eg, effect of medication) will be regarded as women of childbearing potential and required along with the partner of subject enrolled in study to both use adequate contraceptive methods (eg, concomitant use of a spermatocidal agent and barrier contraceptive, intrauterine contraceptive, which are approved or certificated in Japan [for Japanese subjects] and US [for US subjects]) during the study and for at least 7 months after the last dose of U3-1402.

Subjects who wear contact lenses must discontinue wearing their lenses if they have any mild to moderate symptoms (CTCAE Grade  $\leq 2$ ) while receiving treatment until at least 1 week after symptoms have resolved. If a subject has a recurrence of eye symptoms or experiences any severe (CTCAE Grade  $\geq 3$ ) ocular events they must discontinue wearing their contact lenses until at least 1 week after treatment is permanently discontinued. Subjects must not use any eye drops or ointment for treatment of eye symptoms, unless agreed by a study doctor, at any time during the study and  $\geq 1$  week after permanent discontinuation of study treatment.

Subjects must avoid using tanning lights and booths. When in the sun, subject should cover their skin and use sunscreen as possible.

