- 10. Male and female subjects of reproductive/childbearing potential must agree to use a highly effective form of contraception or avoid intercourse during the study and for at least 7 months after the last dose of study drug. For the purpose of this protocol, methods considered as highly effective methods of contraception include:
  - a. Combined (estrogen and progestogen containing) hormonal contraception associated with inhibition of ovulation (oral, intravaginal, or transdermal delivery).

- b. Progestogen-only hormonal contraception associated with inhibition of ovulation (oral, injectable, or implantable delivery).
- c. Intrauterine device (IUD).
- d. Intrauterine hormone-releasing system (IUS).
- e. Bilateral tubal occlusion.
- f. Vasectomized partner.
- g. Complete sexual abstinence.

Non-childbearing potential is defined as pre-menopausal with documented tubal ligation or hysterectomy; OR postmenopausal with documented ≥12 months of spontaneous amenorrhea (in questionable cases, a blood sample with simultaneous follicle-stimulating hormone [FSH] >40 mIU/mL and estradiol <40 pg/mL [<140 pmol/L] is confirmatory).

Females on hormone replacement therapy (HRT) and whose menopausal status is in doubt will be required to discontinue HRT and use 1 of the contraception methods outlined above for women of childbearing potential. Otherwise, they must discontinue HRT to allow confirmation of post-menopausal status prior to study enrollment. For most forms of HRT, at least 2 to 4 weeks must elapse between the cessation of therapy and the blood draw; this interval depends on the type and dosage of HRT. Use of HRT is not allowed during the study. Men who are fertile and sexually active should be willing to use highly effective methods of contraception if their partners are of reproductive potential. Male subjects must not freeze or donate sperm starting at Screening and throughout the study period, and at least 4 months

Female subjects must not donate or retrieve, for their own use, ova from the time of Screening and throughout the study treatment period, and for ≥7 months after the final dose of study drug.

11. Is able to provide written informed consent.

after the final study drug administration.

12. Has a life expectancy of  $\geq 3$  months.

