  - Progestogen-only hormonal contraception associated with inhibition of ovulation (oral, injectable, or implantable delivery).
  - Intrauterine device (IUD).
  - Intrauterine hormone-releasing system (IUS).
  - Bilateral tubal occlusion.
  - Vasectomized partner.
  - Complete sexual abstinence.

Non-childbearing potential is defined as pre-menopausal with documented tubal ligation or hysterectomy; OR postmenopausal with documented ≥12 months of spontaneous amenorrhea (in questionable cases, a blood sample with simultaneous follicle-stimulating hormone [FSH] >40 mIU/mL and estradiol <40 pg/mL [<140 pmol/L] is confirmatory).

Females on hormone replacement therapy (HRT) and whose menopausal status is in doubt will be required to discontinue HRT and use 1 of the contraception methods outlined above for women of childbearing potential. Otherwise, they must discontinue HRT to allow confirmation of post-menopausal status prior to study enrollment. For most forms of HRT, at least 2 to 4 weeks must elapse between the cessation of therapy and the blood draw; this interval depends on the type and dosage of HRT. Use of HRT is not allowed during the study. Men who are fertile and sexually active should be willing to use highly effective methods of contraception if their partners are of reproductive potential.

Male subjects must not freeze or donate sperm starting at Screening and throughout the study period, and at least 4 months after the final study drug administration.

Female subjects must not donate or retrieve, for their own use, ova from the time of Screening and throughout the study treatment period, and for  $\geq 7$  months after the final dose of study drug.

- 11. Is able to provide written informed consent.
- 12. Has a life expectancy of  $\geq 3$  months.

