12. Has adequate treatment washout period before enrollment, defined according to the following:

Treatment	Washout period
Major surgery	≥3 weeks
Radiation therapy	≥3 weeks (or 2 weeks for palliative radiation for bone metastasis [excluding pelvic radiation] and brain metastasis, 1 week for stereotactic radiotherapy)
Hormonal therapy	≥2 weeks
Chemotherapy (including antibody drug therapy)	≥3 weeks (≥2 weeks for 5-fluorouracil-based agents, folinate agents, or weekly paclitaxel. ≥6 weeks for nitrosoureas or mitomycin C)
Immunotherapy	≥3 weeks
CYP3A4 strong inhibitor	≥3 elimination half-lives of the inhibitor
QTc-prolonging medications	≥3 elimination half-lives of the medications
OATP1B inhibitor	≥3 elimination half-lives of the inhibitor

- 13. Has at least 1 measurable lesion based on RECIST version 1.1 confirmed by the central laboratory.
- 14. Male and female subjects of reproductive/childbearing potential must agree to use a highly effective form of contraception or avoid intercourse during the study and for at least 7 months after the last dose of study drug. For the purpose of this protocol, methods considered as highly effective methods of contraception include:
  - a. Combined (estrogen and progestogen containing) hormonal contraception associated with inhibition of ovulation (oral, intravaginal, or transdermal delivery).

- b. Progestogen-only hormonal contraception associated with inhibition of ovulation (oral, injectable, or implantable delivery).
- c. Intrauterine device (IUD).
- d. Intrauterine hormone-releasing system (IUS).
- e. Bilateral tubal occlusion.
- f. Vasectomized partner.
- g. Complete sexual abstinence.

Non-childbearing potential is defined as pre-menopausal with documented tubal ligation or hysterectomy; OR postmenopausal with documented ≥12 months of spontaneous amenorrhea (in questionable cases, a blood sample with simultaneous follicle-stimulating hormone [FSH] >40 mIU/mL and estradiol <40 pg/mL [<140 pmol/L] is confirmatory).

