Females on hormone replacement therapy (HRT) and whose menopausal status is in doubt will be required to discontinue HRT and use 1 of the contraception methods outlined above for women of childbearing potential. Otherwise, they must discontinue HRT to allow confirmation of post-menopausal status prior to study enrollment. For most forms of HRT, at least 2 to 4 weeks must elapse between the cessation of therapy and the blood draw; this interval depends on the type and dosage of HRT. Use of HRT is not allowed during the study. Men who are fertile and sexually active should be willing to use highly effective methods of contraception if their partners are of reproductive potential.

Male subjects must not freeze or donate sperm starting at Screening and throughout the study period, and at least 4 months after the final study drug administration.

Female subjects must not donate or retrieve, for their own use, ova from the time of Screening and throughout the study treatment period, and for  $\geq 7$  months after the final dose of study drug.

- 15. Is able to provide written informed consent.
- 16. Has a life expectancy of  $\geq 3$  months.

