After obtaining written informed consent (Section 15.3), the Investigator or designee must determine if all inclusion and exclusion criteria have been satisfied, including obtaining a fresh tumor biopsy, if required. A subject is considered enrolled in the study once the Investigator enters all required data of eligible subjects into the IRT (IWRS). After the confirmation of the eligibility of the subject, the Investigator or designee enters subject data in the IRT. The date of enrollment is defined as the date that the subject is confirmed eligible in the IRT.

When the subject is enrolled, administration dose and dosing schedule will be assigned by the IRT. Investigators must confirm the dosing regimen assigned by the IRT before administration of U3-1402.

For screen fail subjects, Investigators must explain the reason of screen failure to the subject and then record the date of screen failure and the reason of failure in the IRT.

Electronic case report form (eCRF) will be created for all subjects who have signed informed consent for participation in the study. An eCRF will not be created for subjects who have signed informed consent for examination of the tumor only. Data for all study visits will be recorded on the eCRF for subjects who receive study drug. Only minimal data will be recorded as screening failures on the eCRF for subjects who do not meet eligibility and/or do not receive study drug. Further data, such as AEs, will not be collected from subjects once they are considered screen failures or have decided to withdraw prior to receiving study drug.

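### Section 5.6.4 states a lower contraception standard for women than inclusion criteria 10 and 14 over the same period, and does not refer to them

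*Combined protocol and SAP*

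**What the plan says.** Section 5.6.4 (Dietary and Lifestyle Restrictions) is not limited to one study part. It treats women with medically caused amenorrhea of 12 months or more, other than from sterilization surgery, as of childbearing potential. Such a woman and her partner are told "to both use adequate contraceptive methods (eg, concomitant use of a spermatocidal agent and barrier contraceptive". The second example is an intrauterine contraceptive, and the examples are to be approved or certificated in Japan or the US as applicable. The period is "during the study and for at least 7 months after the last dose of U3-1402".

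Inclusion criterion 10 (Section 4.1.1 and synopsis) and criterion 14 (Section 4.1.3 and synopsis) say that male and female subjects able to conceive or father a child "must agree to use a highly effective form of contraception or avoid intercourse during the study and for at least 7 months", counted from the final dose. The list of methods opens with "For the purpose of this protocol, methods considered as highly effective methods of contraception include" and names seven: combined hormonal, progestogen-only hormonal, intrauterine device, intrauterine hormone-releasing system, bilateral tubal occlusion, vasectomized partner, and complete abstinence.

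**The concern.** Two instructions cover the same women over the same months, and they ask for different grades of protection. The grade matters because the released drug derives from a topoisomerase I inhibitor (List of Definitions of Terms). Section 1.2.2.4 also reports reproductive-organ toxicity in rats from 20 mg/kg and ovarian findings in monkeys from 10 mg/kg.

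At entry the stricter rule is applied: under Section 5.1.2.1 "the Investigator or designee must determine if all inclusion and exclusion criteria have been satisfied". The exposure comes later. The number of cycles is not limited (Section 3.1.1.4), and a woman may change method on treatment or in the 7 months afterwards. A site looking in the treatment section for the rule would reach Section 5.6.4, find spermicide plus barrier offered as acceptable, and see no pointer to the criterion.

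**Working it through.** No arithmetic applies, so the check sets the two texts side by side.

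| Element | Section 5.6.4 | Criteria 10 and 14 |
|---|---|---|
| Grade of method | Adequate | Highly effective, or no intercourse |
| Methods named | 2 examples: spermicide with barrier; intrauterine | 7 methods; no spermicide, no barrier |
| Who must act | The woman and her partner | The subject |
| Regional approval | Japan or US | Not mentioned |
| Period | Study plus at least 7 months after last dose | Study plus at least 7 months after last dose |
| Reference to the other text | None | None |

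1. **Period.** It is identical, so timing does not reconcile the two texts.

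2. **Methods.** Of the two examples in Section 5.6.4, the intrauterine one is on the criteria's list and spermicide plus barrier is not. The conflict is confined to that example and to the word *adequate*.

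3. **Number of wordings.** The criterion text appears in four places (criteria 10 and 14, each in the synopsis and in Section 4.1), but it is one text repeated. The comparison is between two wordings and should not be counted as four against one.

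4. **Is the list closed?** Not expressly, because it is introduced by a word meaning that it includes the items. Nothing in the documents, however, classes spermicide plus barrier as highly effective. Section 4.1.1 also tells certain women to "use 1 of the contraception methods outlined above for women of childbearing potential". That sentence is limited to women on hormone replacement therapy whose menopausal status is in doubt. It shows the list serving as the reference in that case only.

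5. **Men.** Section 4.1.3 says "Men who are fertile and sexually active should be willing to use highly effective methods of contraception if their partners are of reproductive potential", and criterion 10 says the same. Section 5.6.4 is therefore the only contraception instruction that uses the lower grade.

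6. **Which text governs?** The criterion does. Its own period runs through the study and for 7 months after the last dose, and Section 15.5 allows no waiver of stated criteria except to remove an immediate hazard to the subject.

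**The case against.** The strongest reply is that nothing has been relaxed. The criterion binds throughout, and Section 5.6.4 can be read as an addition: it places a duty on the woman's partner that the criteria do not, and its examples are only examples. A couple can satisfy both texts with a highly effective method plus use by the partner. On this view, all that is missing is a cross-reference. Most of this stands. What it does not answer is that a wider circle of people with a duty does not raise the grade of method. A couple relying on spermicide plus barrier would match the section's own example while the woman fell short of the criterion.

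A second reply is that the harm is conjectural. It requires a change of method after entry and a site that consults this section alone. Subjects would probably receive their instructions through consent material, which is not in the copy reviewed. This also stands as a limit on weight: if the consent form carries the highly effective list, the practical gap largely closes.

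Third, there are backstops: pregnancy tests at screening and end of treatment (Sections 6.1 and 6.7), pregnancy as a reason for withdrawal (Section 5.7.1), and pregnancy reporting up to 7 months after discontinuation (Section 8.7). They detect pregnancy and do not prevent it. No pregnancy test is scheduled between screening and end of treatment, and the routine follow-up visit falls 28 days after the last dose (Section 6.8), well short of 7 months.

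**Conclusion.** The point holds as a minor correction to a safety instruction. The protocol has two wordings of unequal strength for the same period, and the weaker one sits in the treatment section without a pointer to the stronger. It applies to women regarded as of childbearing potential in all three parts. The documents do not give their number, and it may now be small because the study period is planned to end on 31 Dec 2023 (Section 17.2.2). No endpoint, estimate or analysis is affected.

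Three stronger readings are tempting and are not supported:

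- A reader might infer that Section 5.6.4 replaces the criterion and permits spermicide plus barrier alone. Nothing in it says so, and the criterion continues to govern.
- A reader might infer that the criteria expressly forbid every unlisted method. The list is not worded as exhaustive.
- A reader might infer that subjects were in fact less well protected. The documents contain no evidence on this.

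The conclusion assumes only that sites may consult Section 5.6.4 after enrollment and that the consent wording, which could not be seen, does not already settle the matter.

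**What to change.** In Section 5.6.4, replace the phrase on adequate methods and its examples with: *a highly effective method of contraception as described in inclusion criterion 10 (Section 4.1.1) or 14 (Section 4.1.3), or avoid intercourse*. Delete spermicide plus barrier as a sufficient example.

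Keep the other elements of the clause: the rule on medically caused amenorrhea, the Japan or US approval condition where it applies, the 7-month period, and the partner's duty. The partner's duty should not become optional in the rewrite. Add a sentence saying that a barrier method used by the partner is in addition to the highly effective method and not instead of it. Check that the consent wording matches.

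The cost is one clause at the next amendment and a consistency check of the consent form. Visits, tests, data collection and analysis do not change.

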# 5.7. Subject Withdrawal/Discontinuation

#### 5.7.1. Reasons for Withdrawal

Any subject who discontinues from the study treatment for any reason will have their study treatment discontinuation recorded.

Subjects may be withdrawn from the study after signing informed consent for the following reasons:

- Progressive disease (PD) per RECIST version 1.1
- Clinical progression: provide date (ie, definitive clinical signs of disease progression, but a recent radiographic assessment did not meet the criteria for PD according to RECIST version 1.1)
- AE
- Death
- Pregnancy
- Withdrawal of consent by subject
- Lost to follow-up
- Protocol violation (specify)
- Study terminated by Sponsor
- Other, specify (eg, Investigator discretion)

If there is evidence that the subject is receiving benefit from treatment even though the subject has met a criterion for discontinuation as listed above, the subject may remain on study treatment after discussion with and approval from the Sponsor.

Discontinued subjects will be followed for survival, either through direct contacts or by collecting public records (eg, death certificates) as allowed by local laws.

